## **8. CONCOMITANT MEDICATION AND TREATMENT**

### **8.1. Concomitant medication**

All concomitant medication(s), including over the counter drugs, blood products etc., administered to patients from baseline up until the safety follow-up visit must be reported in the Case Report Form (CRF).

Corticosteroids administered to the patient for disease control must be reported in the CRF. Dosage, frequency, dates of administration, and route of administration must be recorded in the dedicated CRF pages.

Any diagnostic, therapeutic or surgical procedure performed during the study treatment period must be recorded with corresponding dates, description and any clinical findings.

## **8.2. Not permitted concomitant treatment**

The following treatments are **NOT** permitted:

- Bevacizumab or re-irradiation will not be allowed in the treatment phases of the study and will be considered as evidence of disease progression.

– Treatment with other systemic anti-cancer agents before disease progression has been confirmed (chemotherapy, hormonal therapy, immunotherapy, vaccines, targeted agents, retinoic acids, or other treatments not part of protocol-specified anti-cancer therapy)

– Concurrent investigational agents of any type before disease progression has been confirmed

– Any medications contraindicated with the chemotherapy regimen (temozolomide) are not permitted and special warnings and precautions for the use of temozolomide should be observed (as long as the patient receives temozolomide)

– Intra-tumoral interstitial therapy, or any form of radiosurgery

Any of the above will lead to patient's discontinuation from study treatment.

## **8.3. Anticoagulation**

Use of full-dose anticoagulants is permitted as long as at the time of baseline the INR (or PT [secs]) and aPTT are within therapeutic limits (according to the medical standard in the institution) AND the patient has been on a stable dose of anticoagulants for at least two weeks.

During the study, the preferred choice for anticoagulation treatment with therapeutic intent should be low molecular weight heparin as per ASCO guidelines. In this case, levels of anti-Xa should be within the therapeutic range.

Caution should however, always be exercised, patients adequately supervised, and all anti-coagulant medications recorded in the appropriate CRF page.

If a patient suffers a thromboembolic event, it may be possible for him/her to remain on study treatment.

## **8.4. Supportive care guidelines**

– Supportive care therapy (e.g. antiemetic, antidiarrheal, hydration, etc.) should be prescribed according to local practice.

– Use of colony-stimulating factors (e.g., G-CSF, GM-CSF, erythropoietin, etc.) in a manner consistent with product labeling is discouraged but permitted at the discretion of the Investigator or treating oncologist. However, G-CSF and other colony stimulating factors should not be administered to allow temozolomide administration at a higher dose or to avoid temozolomide interruption during the radiotherapy.

– The duration of treatment with the maximum dose of 12 mg should be no more than 7 consecutive days. The investigator(s) should make every effort to taper the Dexamethasone as soon as symptom improvement allows to the lowest tolerable dose that controls the CNS symptoms. Corticosteroid use for iAE's will be done according to the treatment algorithms in the appendix. The use of other immunosuppressant such as rituximab, etc. will not be allowed and will lead to study withdrawal due to study drug immune related adverse event (iAE).

Changes in corticosteroid dosage will be discouraged in the period 2 weeks prior to the 12 months MRI or CT scan.

Patients who for control of peritumoral edema require doses of dexamethasone greater than 12mg/day or its equivalent or for periods longer than 7 days will be considered as having disease progression unless this occurs within the first 3 months of the study.

Bevacizumab or re-irradiation will not be allowed in the study.

Antiepileptic therapy will be allowed if required. The choice of antiepileptic agent will be according to best medical fit for each patient. Hepatic enzyme inducers should however be avoided.

Upon confirmation of disease progression as per the new iRANO criteria, (see section) patients will be treated at the investigator or local oncologist's discretion. Patients who have confirmed radiological progression without evidence of study drug toxicity will at the investigator and patient's discretion be allowed to continue with study drug. All subjects will be followed for survival data collection and information about subsequent therapies will be collected. Tissue samples in patients undergoing second surgical resections will be obtained for further biomarker analysis.

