## **10. INVESTIGATIONAL MEDICINAL PRODUCT**

### **10.1. Dose and Schedule of Test Drug**

Avelumab is a fully human IgG1 antibody directed against PD-L1. Avelumab binds PD-L1 and blocks the interaction between PD-L1 and its receptors PD-1 and B7.1. This removes the suppressive effects of PD-L1 on anti-tumor CD8+ T cells, resulting in the restoration of cytotoxic T cell response.

Avelumab will be administered intravenously every 14 days starting the same day as the first day of the first 5 days po temozolomide treatment. Temozolomide's 28 days cycle will be repeated 6 times or until grade 3 or higher temozolomide related treatment AE's. Avelumab will be continued IV q14 days for 260 weeks or until grade 3 or higher avelumab treatment-related AE's occurs and independent of whether the patient continues or completes the 6 cycles of temozolomide.

Avelumab may be withheld temporarily in the case of irAE according to the irAE's algorythms (table 3)

Temozolomide dose may be adjusted or withheld according to the directives in the temozolomide's product monograph (appendix 4)

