## Assessment and Initial Management of Tumor Lysis Syndrome

## 11.6. Immune related Adverse Event (irAE)

Immune checkpoint inhibitors are known to cause autoimmune adverse events. Previous studies with avelumab has shown an incidence of 9.7% most of them of grade 2 severity.

Any untoward medical occurrence, sign/symptom, disease, including laboratory abnormality or exacerbation of previous condition occurring during the study drug and believed to be of autoimmune origin will be classified as an immune related/emergent autoimmune adverse event (irAE).

Treatment of irAE's is mainly dependent upon severity (NCI-CTCAE grade):

Grade 1 to 2: treat symptomatically or with moderate dose steroids, more frequent monitoring

Grade 1 to 2 (persistent): manage similar to high grade AE (Grade 3 to 4)

Grade 3 to 4: treat with high dose corticosteroids

Treatment of irAEs should follow guidelines set forth in the table below (table 3).

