**Table 3: Management of Immune-mediated Adverse Reactions**

Since inhibition of PD-L1 stimulates the immune system, immune-related AEs (irAEs) may occur. Treatment of irAEs is mainly dependent upon severity (NCI-CTCAE grade):

Grade 1 to 2: treat symptomatically or with moderate dose steroids, more frequent monitoring

Grade 1 to 2 (persistent): manage similar to high grade AE (Grade 3 to 4)

Grade 3 to 4: treat with high dose corticosteroids

Treatment of gastrointestinal, dermatological, pulmonary, hepatic and endocrine irAEs should follow guidelines set forth in the table below Table 4.

Gastrointestinal irAEs		
Severity of Diarrhea / Colitis (NCI-CTCAE v4.03)	Initial Management	Follow-up Management
Grade 1 Diarrhea: < 4 stools/day over Baseline Colitis: asymptomatic	Continue avelumab therapy Symptomatic treatment (for example, loperamide)	Close monitoring for worsening symptoms Educate subject to report worsening immediately If worsens: Treat as Grade 2, 3 or 4

Grade 2
 
Diarrhea: 4 to 6 stools per day over Baseline; IV fluids indicated < 24 hours; not interfering with ADL
 
Colitis: abdominal pain; blood in stool
	
withhold avelumab therapy
 
Symptomatic treatment
	
If improves to Grade <math>\leq</math> 1: Resume avelumab therapy
 
If persists > 5 to 7 days or recur: Treat as Grade 3 to 4

Grade 3 to 4
 
Diarrhea (Grade 3): <math>\geq</math> 7 stools per day over Baseline; incontinence; IV fluids <math>\geq</math> 24 hrs.; interfering with ADL
 
Colitis (Grade 3): severe abdominal pain, medical intervention indicated, peritoneal signs
 
Grade 4: life-threatening, perforation
	
withhold avelumab for Grade 3
 
Permanently discontinue avelumab for Grade 4 or recurrent Grade 3
 
1.0 to 2.0 mg/kg/day methylprednisolone IV or equivalent
 
Add prophylactic antibiotics for opportunistic infections
 
Consider lower endoscopy
	
If improves: Continue steroids until Grade <math>\leq</math> 1, then taper over at least 1 month. Resume Avelumab therapy following steroids taper (for initial grade 3).
 
If worsens, persists > 3 to 5 days, or recurs after improvement: Add infliximab 5 mg/kg (if no contraindication), Note: Infliximab should not be used in cases of perforation or sepsis

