Grade 3 to 4 Grade 3: Severe new symptoms; New / worsening hypoxia; Grade 4: life-threatening	
Permanently discontinue avelumab therapy
 
Hospitalize
 
Pulmonary and Infectious Disease consults
 
1.0 to 2.0 mg/kg/day prednisone or equivalent
 
Add prophylactic antibiotics for opportunistic infections
 
Consider bronchoscopy, lung biopsy
	
If improves to Grade <math>\leq</math> 1:
 
Taper steroids over at least 1 month
 
If not improving after 48 hours or worsening:
 
Add additional immunosuppression (for example, infliximab, cyclophosphamide, IV immunoglobulin, or mycophenolate mofetil)

Hepatic irAEs		
Grade of Liver Test Elevation (NCI-CTCAE v4)	Initial Management	Follow-up Management
Grade 1 Grade 1 AST or ALT > ULN to 3.0 x ULN and / or total bilirubin > ULN to 1.5 x ULN	Continue avelumab therapy	Continue liver function monitoring If worsens: Treat as Grade 2 or 3 to 4
Grade 2 AST or ALT > 3.0 to $\leq$ 5 x ULN and / or total bilirubin > 1.5 to $\leq$ 3 x ULN	Withhold avelumab therapy Increase frequency of monitoring to every 3 days	If returns to Grade $\leq$ 1: Resume routine monitoring, resume avelumab therapy If elevations persist > 5 to 7 days or worsens: Treat as Grade 3 to 4
Grade 3 to 4 AST or ALT > 5 x ULN and / or total bilirubin > 3 x ULN	Permanently discontinue avelumab therapy Increase frequency of monitoring to every 1 to 2 days 1.0 to 2.0 mg/kg/day prednisone or equivalent Add prophylactic antibiotics for opportunistic infections Consult gastroenterologist/hepatologist Consider obtaining MRI/CT scan of liver and liver biopsy if clinically warranted	If returns to Grade $\leq$ 1: Taper steroids over at least 1 month If does not improve in > 3 to 5 days, worsens or rebounds: Add mycophenolate mofetil 1 gram (g) twice daily If no response within an additional 3 to 5 days, consider other immunosuppressants per local guidelines
Renal irAEs		
Grade of Creatinine Increased (NCI-CTCAE v4)	Initial Management	Follow-up Management
Grade 1 Creatinine increased > ULN to 1.5 x ULN	Continue avelumab therapy	Continue renal function monitoring If worsens: Treat as Grade 2 to 3 or 4.

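### Section 8.4 disallows non-steroid immunosuppressants for immune-related events, Table 3 directs or permits them, and nothing expressly lifts the ban

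*Protocol*

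**What the plan says.** Protocol Section 8.4 (Supportive care guidelines) deals with steroids for immune-related events first: "Corticosteroid use for iAE's will be done according to the treatment algorithms in the appendix". The next sentence sets the rule for everything else: "other immunosuppressant such as rituximab, etc. will not be allowed and will lead to study withdrawal due to study drug immune related adverse event".

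Section 11.6 gives a different instruction for the same events: "Treatment of irAEs should follow guidelines set forth in the table below (table 3". Section 10.1 also places the algorithms there: "Avelumab may be withheld temporarily in the case of irAE according to the irAE's algorythms (table 3".

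In its Grade 3-4 gastrointestinal row, Table 3 says that if the event worsens, persists beyond 3 to 5 days "or recurs after improvement: Add infliximab 5 mg/kg (if no contraindication". In its Grade 3-4 pulmonary row the trigger is "If not improving after 48 hours or worsening" and the instruction is "Add additional immunosuppression (for example, infliximab, cyclophosphamide, IV immunoglobulin, or mycophenolate mofetil". The Grade 3-4 hepatic row adds mycophenolate mofetil after more than 3 to 5 days without improvement, or on worsening or rebound. The myocarditis row allows azathioprine or cyclosporine A to be considered. The row for other Grade 4 irAEs allows a further immunosuppressant as needed.

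**The concern.** Staff treating an immune event that has not responded to steroids find one section disallowing a class of drug and another section's table telling them to add a member of it. The ban is not limited to rituximab: the wording makes rituximab an example and leaves the list open. It names the irAE as the reason for withdrawal, so irAE treatment is within its scope.

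Two things are at stake. The first is whether the rescue drug may be given at all. The second is the patient's status afterwards. Section 8.4 speaks of withdrawal from the study, and elsewhere the protocol separates that from stopping treatment. Section 8.2 uses discontinuation from study treatment as the consequence of other prohibited therapies. Section 9.3.4 singles out patients who end treatment and also leave the study. Under Section 6.2 a withdrawn patient is followed for survival only with permission and is otherwise treated as lost to follow-up. The primary objective is safety, and these would be the patients with the most serious immune toxicity.

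**Working it through.** No figure in the plan is in dispute, so the check sets the texts side by side and then asks what follows for the primary endpoint.

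**1. What Table 3 does in each row that names a rescue drug**

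| Table 3 row | Rescue drug | Status of the instruction | Avelumab by that point |
|---|---|---|---|
| Gastrointestinal, Grade 3-4 | Infliximab | Directed | Withheld (Grade 3); stopped permanently (Grade 4 or recurrent Grade 3) |
| Pulmonary, Grade 3-4 | Infliximab, cyclophosphamide, IV immunoglobulin or mycophenolate, as examples | Directed | Stopped permanently |
| Hepatic, Grade 3-4 | Mycophenolate, then other agents | Directed, then permitted | Stopped permanently |
| Immune-related myocarditis | Azathioprine or cyclosporine A, as examples | Permitted | Stopped permanently |
| Other irAEs, Grade 4 | Other immunosuppressant | Permitted | Stopped permanently |

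Section 8.4 disallows the class in all five rows.

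**2. Is there a rule on which text prevails?** Section 11.6 points to Table 3 as the irAE guide, but neither it nor Table 3 mentions the 8.4 ban. Section 8.4 makes no exception for Table 3. It refers only corticosteroid use to algorithms, and it places them in the appendix. Appendices 1 to 5 as supplied cover the iRANO algorithm, Karnofsky status, MRI parameters, temozolomide dosing and ECOG status. None is an irAE algorithm, so that cross-reference is also wrong.

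**3. Does the emergency clause settle it?** Section 11.12 covers emergencies that need immediate attention. Table 3 also triggers rescue drugs after 48 hours without improvement (pneumonitis) or after 3 to 5 days (colitis, hepatitis). Those are planned escalations that the clause does not clearly reach.

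**4. Effect on the primary endpoint.** Sections 5.1 and 12.3.1 count permanent and transient discontinuations of avelumab together. By the last column above, avelumab has been withheld or stopped in every row before a rescue drug is given. The patient is counted whichever text is followed, so the change in the pooled count is 0.

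**5. How often could it arise?** Section 2 gives counts of treatment-related Grade 3 or higher events in the pooled expansion cohort of 1300:
- pneumonitis 4: 4/1300 = 0.3%
- autoimmune hepatitis 4: 4/1300 = 0.3%
- colitis 3: 3/1300 = 0.2%

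The Grade 3-4 hepatic row is triggered by AST or ALT above 5 times the upper limit of normal, or bilirubin above 3 times, and does not require a diagnosis of autoimmune hepatitis. Section 2 also lists Grade 3 or higher AST increased (5), ALT increased (3) and transaminases increased (3), any of which could meet that trigger. It does not say how many patients had more than one of these events, and it gives no count for myocarditis. Nor do the documents say what share of events fails steroids. The calculation stops here.

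**The case against.** The strongest reply is that 8.4 states a consequence and does not refuse treatment. A drug that is never given cannot lead to withdrawal, so the sentence expects use and says what follows. Section 8.2 works the same way: it lists treatments as not permitted and then says what happens if one is used. On this reading, four of the five rows end avelumab under both texts. This narrows the conflict but does not remove it, because 8.4 says both that the drug is not allowed and that the patient leaves the study.

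The second reply is that Section 11.6 is the specific section on irAEs and 8.4 is general supportive care, so Table 3 should govern. That is the sensible reading and much of it stands: most investigators would follow Table 3. It remains an inference, since 11.6 does not address the ban.

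The third reply is that follow-up is already secured. Section 4.2 puts anyone who stops avelumab for any reason into a 90-day safety phase. Section 9.3.7 follows all who stop treatment for survival. Sections 6.2 and 9.3.4 seek survival calls even from those who leave the study, and the heading in 6.2 uses the two terms loosely. This also stands in part. A reader might infer that 8.4 would lose outcome data, but the documents do not show that. They show only that the patient's status is unclear.

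A reader might also add the pneumonitis, hepatitis and colitis counts and treat the sum as an upper limit on patients at risk, or multiply it by an assumed rate of steroid failure. Neither is supported. The sum omits liver-enzyme events that could meet the hepatic trigger, and the documents offer no basis for any failure rate.

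Finally, a reader might fold in whether avelumab may restart after infliximab. Table 3's gastrointestinal row says "Resume Avelumab therapy following steroids taper (for initial grade 3" in the branch for patients who improve, and its infliximab branch is silent. But Section 11.4 requires permanent discontinuation for Grade 3 events, and neither colitis nor diarrhea is among its exceptions. Restarting after Grade 3 colitis is therefore a separate conflict between 11.4 and Table 3, and it does not belong to this point.

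**Conclusion.** The conflict is real and minor. Taken literally, Section 8.4 forbids rescue drugs that Table 3 directs in three rows and permits in two. It also prescribes study withdrawal where Sections 4.2 and 9.3.7 provide for stopping avelumab with follow-up. Section 11.6 makes Table 3 the more specific guide but does not expressly override the ban.

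The pooled primary count is unchanged and no effect on another analysis is shown. The situation is expected to be rare, judging by the Section 2 counts and assuming that experience with avelumab outside this trial carries over to its use with temozolomide. No probability of rescue use in the 30 patients can be drawn from the documents. Rarity limits how much the point weighs. The rule would still be needed when a patient has a serious event that steroids have not controlled.

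**What to change.** Amend Section 8.4 in three places:

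- State that immunosuppressants other than corticosteroids are permitted when given according to Table 3 for an irAE, and are otherwise prohibited.
- Replace study withdrawal with discontinuation of avelumab as Table 3 and Section 11.4 require, with safety and survival follow-up continuing under Sections 4.2 and 9.3.7.
- Change the reference from the appendix to Table 3.

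The cost is a few words in one protocol amendment. No procedures, patients or analyses are added. Whether avelumab may resume after Grade 3 colitis should be handled separately, by reconciling Section 11.4 with Table 3.

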## **9. SCHEDULE OF ASSESSMENTS AND PROCEDURES**

The type of assessments to be performed and their timing in the respective study periods are summarized in Table 1

### **9.1. Screening Examination and Eligibility Screening Form**

All patients will provide written informed consent (IC) before any study specific procedure is performed.

An eligibility screening form (ESF) documenting the patient's fulfillment of the entry criteria, must be completed by the investigator/designee for all patients considered for the study and subsequently included or excluded from participation. Patients who are considered for study entry, but fail to meet the eligibility requirements, should also have an ESF completed with the non-eligibility reason given (it provides information on the selected trial population). This information will not be entered on the clinical trial database but will be collected with the reason for screen failure. All ESFs should be kept in the study files at the sites.

A CRF will only be completed for patients fulfilling the entry criteria.

## **9.2. Procedures for Enrolment of Eligible Subjects**

Once a subject has fulfilled the entry criteria a subject Enrolment and Identification Code will be attributed and inscribed in the Enrolment and Identification Code List. The latter must be maintained by the investigator.

Baseline evaluation and start of treatment should occur on the same day. When this is not feasible, the delay between baseline evaluation and start of treatment must be kept to a minimum and should not exceed 7 days.

## **9.3. Clinical Assessments and Procedures**

### **9.3.1. Screening and Baseline Procedures**

All screening and baseline study related activities are summarized in table1. All patients should provide written informed consent before any study specific procedures are performed.

#### **9.3.1.1. Screening Assessments**

Must occur between weeks -12 and -1 of the baseline visit

Demographics and medical history, which include:

- previous and current diseases
- history of glioblastoma, including date of diagnosis, history of prior low grade astrocytoma, location of disease, details of surgery performed
- all medication and surgeries over the last 1 month prior to inclusion into the study (including all over the counter and herbal remedies).
- neurological examination
- signs and symptoms related to GBM
- a complete physical examination, which includes vital signs (sitting blood pressure and body temperature), physical measurements (body weight and height)
- hematology, blood chemistry and urine analysis, a urine dipstick test, coagulation parameters within weeks -2 and week -1 of the baseline visit
- a serum β-HCG test should be performed for all women with an intact uterus (unless amenorrhoeic for the last 24 months).
- the Karnofsky performance score (KPS) within 2 weeks of the baseline visit.
- a P300 evoked potential within 2 weeks of baseline visit
- a study specific gadolinium enhanced MRI or CT scan within 2 weeks of baseline visit
- the corticosteroid dosage must be noted

**NOTE:** In case of a delay of the first dose of study treatment, then any assessments required to meet study entry criteria (P300 and MRI or CT scan expected) have to be repeated if more than 2 weeks have elapsed.

#### **9.3.1.2. Assessments at Baseline**

The baseline visit and the start of treatment will occur on the same day. If not possible then a delay of no more than 7 days will occur between the two.

Assessments will be as specified in the schedule of visits in table 1  
Once the study entrance criteria are reconfirmed patients will receive their first dose of the avelumab.

Vital signs and a pre infusion questionnaire will be done with the infusion nurse prior to starting infusion.

Patients will receive the first dose of the five day course of temozolomide according to standard therapy that same evening and for the subsequent 4 evenings.

